7.3.1. Safety Reporting to Competent Authorities and Ethics Committees

As noted in Section 7.4.2 of Volume 9A of The Rules Governing Medicinal Products in the European Union-Guidelines on Pharmacovigilance for Medicinal Products for Human Use,⁵ it is the MAH's responsibility to report all SADR that occurred within the EU to the Competent Authority of the Member States on whose territory the SADR occurred; this report must be made no later than 15 calendar days following the receipt of information regarding an SADR.

The study physician will be provided with instructions to help comply with all site-specific requirements regarding SADR and ADR reporting, including prompt notification to their IEC of any safety reports and filing of copies of all related correspondence in the patients' notes. Unless otherwise requested by particular IECs, the MAH will normally aim to submit reports to the IECs in the same time frame that these reports are provided to the EMA and CHMP.

8. REGISTRY PROCEDURES

All treatment decisions, including medications, are at the sole discretion of the treating physician in accordance with their usual care. Registry participation does not entail dispensing of study medication or protocol-specified procedures.

8.1. Schedule of Assessments

The currently authorised SPC for Esbriet recommends liver function test monitoring prior to beginning Esbriet, every month for the first 6 months of Esbriet therapy, and every 3 months

thereafter. Scheduled registry visits will occur at baseline and at 3-month intervals for the duration of follow-up. The registry will permit a window of ± 4 weeks around the scheduled visit date. SADRs, ADRs of special interest, Esbriet discontinuations, and registry withdrawals should be reported in a continuous ongoing manner at any time during follow-up.

9. DATA ANALYSIS AND STATISTICAL CONSIDERATIONS

9.1. Sample Size

The registry aims to enrol 1,000 patients with IPF across participating EU Member States. The sample size was selected in order to have sufficient statistical precision as expressed by a 2-sided, 95% confidence limit around the expected incidence rate for each ADR.

The incidence of ADRs during the 75 weeks of exposure among 789 unique patients treated with Esbriet in Phase 3 studies and 2 open-label studies ranged from 2.5% to 22%.

Table 2 shows the precision with a sample size of 1000 for varying rates of ADRs. Precision is defined as half the width of the 95% confidence interval. For example, if the expected proportion of abnormal LFT is 2.5% for a sample size of 1,000, the precision is 0.97%. The precision shown in the table was calculated based on 95% normal approximation confidence interval. The calculation of the confidence intervals was performed using PASS software⁶.

Table 2: Precision for Estimates of ADRs of Varying Proportions with Sample Size of 1000

Expected proportion	Precision
0.5%	0.44%
2.5%	0.97%
5.0%	1.35%
7.5%	1.63%
10.0%	1.86%
15.0%	2.21%
20.0%	2.48%
25.0%	2.68%

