4.2. Setting

The registry aims to initially enrol patients from approximately 100 pulmonary clinics throughout selected EU Member States and is open to all patients who will receive Esbriet. Enrolment will stop when 1,000 patients with a diagnosis of IPF have been enrolled. It is estimated that the enrolment will be completed within approximately 24 months. The MAH will closely monitor enrolment and will keep the Rapporteur and Co-Rapporteur informed of progress with the registry at regular intervals. If progress is not satisfactory, then the MAH will discuss with the Rapporteur and Co-Rapporteur any contingency that might be considered in order to increase the recruitment level in the context of the overall usage of the product within the EU. These may include, but are not limited to, extending the registry into another Member State, opening up more sites and intensifying the communication plan.

Each patient will be followed for up to 2 years. The MAH will also closely monitor the retention of patients and will undertake all reasonable efforts and methods to minimize loss to follow-up for the entire duration of the registry. Treating physicians will collect pre-specified data at the baseline and every 3 months thereafter, for the duration of the patients' participation in study.

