7.1. Definition of Adverse Drug Reactions and Serious Adverse Drug Reactions

An ADR is a noxious and unintended response to a medicinal product related to any dose in which a causal relationship between the medicinal product and the adverse event is at least a reasonable possibility. Therefore all SADR and events of interest that are considered at least possibly related to Esbriet will be defined and collected as ADRs.

An SADR is defined as any ADR meeting the following criteria at any dose:

- Results in death;
- Is life threatening (i.e., the patient was, in the opinion of the physician, at immediate risk of death from the event as it occurred); it does not refer to an event which hypothetically might have caused death if it were more severe;
- Requires or prolongs patient's hospitalization;
- Results in persistent or significant disability/incapacity (i.e., the event causes a substantial disruption of a person's ability to conduct normal life functions);
- Results in a congenital anomaly/birth defect;
- Is an important and significant medical event that may not be immediately life threatening or resulting in death or hospitalization but, based upon appropriate medical judgment, may jeopardize the patient or may require intervention to prevent one of the outcomes listed above.

If there is doubt as to whether the event under consideration is a SADR, the event should be treated as a SADR. If the onset of an event occurred before the patient entered the registry in the context of any pre-planned hospitalization (e.g., for cosmetic treatments or for a pre-existing condition) the event should be classified as serious only if in the view of the physician the hospitalization was prolonged or the pre-existing condition worsened as a result of Esbriet treatment.

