1. SADR
2. Clinically significant ADRs of special interest: These ADRs of special interest encompass all "important identified risks" and "important potential risks" as defined in the Esbriet Risk Management Plan and include:
 - Photosensitivity reactions and skin rashes
 - Abnormal liver function tests
 - Dizziness
 - Weight loss

- Gastrointestinal symptoms
 - Fatigue
 - Falls
 - Drug interactions (including smoking)
 - Increased platelet counts
 - Specific cardiac events: supraventricular tachyarrhythmia, atrioventricular block/sick sinus syndrome, ventricular arrhythmia, bundle branch block, aortic or pulmonic valvular incompetence
 - Blood dyscrasias: agranulocytosis, leukopenia, neutropenia
 - Angioedema
 - Any other clinically significant ADRs based on the judgment of the prescriber
3. Information to be collected in association with reported ADRs (including, but not limited to):
- a. Prescribed Esbriet dose changes and reasons for change
 - b. Concomitant medications including treatments for IPF (those stopped or started within 28 days prior to the event). The following minimum data elements will be collected:
 - Medication name
 - Dose and duration of exposure
 - Indication for use
 - c. Relevant laboratory and clinical tests

In the event that a patient discontinues Esbriet treatment, all SADRs, and ADRs of special interest will be collected until 28 days after the last dose of Esbriet. All serious and reportable ADRs will be followed until resolution or until the end of the follow-up period, whichever comes first.

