9.2.3. Primary Analyses

Cumulative incidence of SADRs, and ADRs of special interest will be calculated as the number of patients who have a specific event starting during the study period, divided by the number of patients enrolled, multiplied by 100.

Risk of SADRs, and ADRs of special interest will be estimated as number of events over cumulative time at risk. Time at risk will be defined as the time between dates of first dose of Esbriet to end of follow-up (completion of follow-up / registry withdrawal). Case narratives will be provided for each SADR.

Tables with counts of SADRs, and ADRs of special interest summarized by MedDRA SOC and PT, and stratified by fatal or non-fatal outcome will be provided. Analysis will be conducted, if possible, for subgroups of patients including: predisposing conditions for liver disease; concomitant immunosuppressive therapy and other therapy for IPF; advanced stages of IPF; secondary cause of pulmonary fibrosis; QT prolongation; underlying cardiac, hepatic and other forms of pulmonary disease; Esbriet use for conditions other than IPF; paediatric patients, and patients who have stable warfarin anticoagulation at the beginning of pirfenidone treatment.

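### Table 2 states precision as if 1,000 patients from about 100 clinics were independent; any between-clinic correlation in ADR reporting makes its half-widths too narrow

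*Protocol*

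**What the plan says.** Protocol section 9.1 sets the target: "The registry aims to enrol 1,000 patients with IPF across participating EU Member States". The only reason given for that number is "sufficient statistical precision as expressed by a 2-sided, 95% confidence limit around the expected incidence rate for each ADR". The section then fixes the measure, "Precision is defined as half the width of the 95% confidence interval", and the method, "The precision shown in the table was calculated based on 95% normal approximation confidence interval". Table 2 lists half-widths for eight expected proportions from 0.5% to 25%, and the text takes abnormal liver function tests at 2.5% (0.97 points) as its example.

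On where the patients come from, section 4.2 says "The registry aims to initially enrol patients from approximately 100 pulmonary clinics throughout selected EU Member States". On what counts as an event, section 7.1 says "all SADR and events of interest that are considered at least possibly related to Esbriet will be defined and collected as ADRs". Section 7.2 limits the ADRs of special interest to clinically significant ones and ends its list with "Any other clinically significant ADRs based on the judgment of the prescriber". Section 7.3 has the physician or site staff identify reportable ADRs, and section 8 says that the registry specifies no procedures of its own. The estimate that Table 2 supports is a crude pooled percentage (section 9.2.3): "number of patients who have a specific event starting during the study period, divided by the number of patients enrolled, multiplied by 100".

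The protocol nowhere mentions clustering, a design effect or variation between clinics.

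**The concern.** A simple binomial half-width is right for independent patients. Here patients share a clinic, about ten to each, and with it the assessor, the threshold for calling an event drug-related or clinically significant, and local testing habits. The protocol's own example is exposed to this. Table 1 schedules liver function tests at baseline only. Later results enter the data only alongside a reported ADR, and monitoring during treatment is a product-label recommendation carried out as usual care (section 8.1). Whether an abnormal result is found and recorded thus depends partly on the clinic.

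There is no control arm and no within-clinic contrast, so variation between clinics goes undiminished into the variance of the pooled proportion. No hypothesis is tested, and precision is the sole justification for the sample size. At stake is whether the precision shown in 9.1 is what the registry can be expected to deliver.

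**Working it through.** **Inputs from the protocol.** N = 1,000, two-sided 95%, normal approximation (9.1); about 100 clinics (4.2), so the mean clinic size is m = 1,000/100 = 10.

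**Inputs assumed, because the protocol gives neither.** ICC from 0.01 to 0.10; clinic sizes equal, then uneven with a coefficient of variation (CV) of 0.8.

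**Step 1: reproduce Table 2.** Half-width = 1.96 × √(p(1−p)/1000). For p = 10%: 1.96 × √(0.09/1000) = 1.859 points, against 1.86 in the table. In table order, the eight rows come out at 0.437, 0.968, 1.351, 1.632, 1.859, 2.213, 2.479 and 2.684, all matching to two decimals. The table's arithmetic is correct and its implied design effect is 1.

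**Step 2: allow for clinics of equal size.** Design effect DE = 1 + (m−1) × ICC = 1 + 9 × ICC. Half-widths are multiplied by √DE, the effective n is 1000/DE, and the actual coverage of the unadjusted 95% interval is 2Φ(1.96/√DE) − 1. Half-widths are in percentage points.

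| ICC | DE | √DE | Effective n | Coverage | 2.5% row | 10% row | 20% row |
|---|---|---|---|---|---|---|---|
| 0 (Table 2) | 1.00 | 1.00 | 1,000 | 95% | 0.97 | 1.86 | 2.48 |
| 0.01 | 1.09 | 1.04 | 917 | 94.0% | 1.01 | 1.94 | 2.59 |
| 0.02 | 1.18 | 1.09 | 847 | 92.9% | 1.05 | 2.02 | 2.69 |
| 0.05 | 1.45 | 1.20 | 690 | 89.6% | 1.17 | 2.24 | 2.99 |
| 0.10 | 1.90 | 1.38 | 526 | 84.5% | 1.33 | 2.56 | 3.42 |

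A beta-binomial simulation (100 clinics of 10, ICC 0.05, p of 5%, 10% and 20%) agrees: the unadjusted interval covers about 89–90%, and a clinic-clustered interval about 94–95%.

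**Step 3: uneven recruitment.** DE = 1 + ((1+CV²) × m − 1) × ICC. With CV = 0.8, (1.64 × 10 − 1) = 15.4. At ICC 0.01, DE = 1.154 and half-widths grow by 7%. At ICC 0.05, DE = 1.77, half-widths grow by 33%, effective n is 565 and coverage is 85.9%.

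**Step 4: which ICC is plausible for an uncommon ADR?** The between-clinic standard deviation is √(ICC × p(1−p)). At p = 2.5% it is 1.56 points for ICC 0.01 and 3.49 points for ICC 0.05, that is 62% and 140% of the mean (1.56/2.5 and 3.49/2.5). The first is already large heterogeneity and the second is strained. For this row the lower end (0.97 to about 1.01–1.05) is the more credible range.

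**The case against.** The strongest reply is that no figure in Table 2 is wrong. The method is disclosed, every row reproduces, no hypothesis is tested and no minimum precision is set. That stands, and it limits the point: the fault is an unstated assumption, not an arithmetic error. A reader might infer that 1,000 patients are too few, but with no precision target the documents do not support that.

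Second, the size is entirely assumed. This also stands. At ICC 0.01 with equal clinics the change is minor. A reader might infer that the 95% limits miss about twice as often as claimed; that holds only near ICC 0.05 (10.4% against 5%), not across the range. Opening more sites, which section 4.2 allows, would lower the mean clinic size, while uneven recruitment would raise the design effect.

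Third, shared procedures reduce differences between clinics: site training, open-ended interview questions and a follow-up algorithm (7.3), the rule to treat doubtful cases as serious (7.1), a common visit schedule (8.1), and possible telephone follow-up by sponsor or contractor staff (6.2). They argue for a lower ICC, but relatedness remains a judgement for every recorded ADR, so they do not justify assuming zero.

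Fourth, section 9.2.3 names no confidence interval, and interval methods are ordinary SAP content. That is fair, and their absence is not criticised here. Nor does any section mention upper limits feeding a risk statement to the regulator, so no consequence of that kind should be inferred. But Table 2 is fixed in the protocol, and a later SAP would not correct it.

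**Conclusion.** The point holds in a conditional form. The precision that alone justifies the sample size assumes independent patients, while the protocol's design gives concrete reasons for patients at one clinic to be alike. The direction is certain for any positive ICC; the size is not known. With ten patients in each of 100 clinics, the understatement of the half-widths runs from 4% (ICC 0.01) to 38% (ICC 0.10), with coverage from about 94% down to 84.5%, and more with uneven clinic sizes. For uncommon ADRs it is probably near the lower end. The stated precision is optimistic and worth correcting, but the conclusion does not reach the adequacy of the sample size or any analysis that the protocol has not fixed.

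**What to change.** Keep N = 1,000. In section 9.1, state that Table 2 assumes independent patients. Add half-widths multiplied by √(1 + (m−1) × ICC) with m = 10, over ICC 0.01 to 0.10, labelled as assumptions. For the 10% row these are 1.94, 2.02, 2.24 and 2.56 points at ICC 0.01, 0.02, 0.05 and 0.10, beside the present 1.86. Note that uneven clinic sizes would widen them further.

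Wherever 95% limits for ADR proportions or rates are reported, use a standard error clustered by clinic, or for rare ADRs an exact interval at the effective n. The SAP is a suitable place for that wording.

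The cost is a sentence and extra columns in 9.1, plus an option in the analysis program; the enrolling clinic should already be on record for each patient. No patients, visits or data are added. The downside is slightly wider stated precision and reported limits.

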3. OBJECTIVE

The objective of this study is to evaluate the long-term safety profile of Esbriet in patients with IPF and to monitor for any unknown or potential risks of treatment with Esbriet.

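### Table 2's 0.5% row rests on a normal approximation that is poor with five expected events, so its single symmetric 0.44% understates the upper uncertainty for uncommon reactions

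*Protocol*

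**What the plan says.** Section 9.1 of the protocol chooses the sample size for precision alone. The aim is "sufficient statistical precision as expressed by a 2-sided, 95% confidence limit around the expected incidence rate for each ADR". Precision has an explicit meaning: "Precision is defined as half the width of the 95% confidence interval". The scope is also explicit: "Table 2 shows the precision with a sample size of 1000 for varying rates of ADRs". The method is disclosed: "The precision shown in the table was calculated based on 95% normal approximation confidence interval".

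The same section cites ADR incidences of 2.5% to 22% over 75 weeks in 789 treated patients. Table 2 runs from 0.5% (precision 0.44%) to 25% (precision 2.68%), so its 0.5% row is the only one below the cited range.

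Uncommon reactions matter to this registry by its own account. Section 3 sets out "to monitor for any unknown or potential risks of treatment with Esbriet", and the ADRs of special interest in Section 7.2 include "Blood dyscrasias: agranulocytosis, leukopenia, neutropenia" and angioedema. The protocol gives no expected rates for these.

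**The concern.** The normal-approximation interval is symmetric about the estimate and takes its variance from the estimate. With few events this works badly. The binomial distribution is skewed, and samples with fewer events than expected also produce intervals that are too short. The misses then pile up on one side, with the upper limit below the true rate.

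For an uncommon harm the upper limit carries most of the information. The 0.5% row is the only figure in Section 9.1 that tells a reader what 1,000 patients can say about a reaction rarer than the cited range, and it is the row where the method is weakest. A reader who takes 0.5% plus or minus 0.44% as a 95% statement will think that an observed 5 in 1,000 excludes rates above about 0.94%. Methods suited to small counts put that limit at about 1.16-1.17%.

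**Working it through.** **Inputs.** From Section 9.1: n = 1,000; 95% two-sided, so z = 1.96; precision is the half-width; normal approximation; p = 0.5% to 25%.

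**Step 1: reproduce Table 2.** Half-width = 1.96 × √(p(1 − p)/n). At p = 0.005 this is 1.96 × √(0.005 × 0.995/1000) = 1.96 × 0.002230 = 0.00437, or 0.44%.

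| Expected proportion | Recomputed half-width | Table 2 |
|---|---|---|
| 0.5% | 0.437% | 0.44% |
| 2.5% | 0.968% | 0.97% |
| 5.0% | 1.351% | 1.35% |
| 7.5% | 1.632% | 1.63% |
| 10.0% | 1.859% | 1.86% |
| 15.0% | 2.213% | 2.21% |
| 20.0% | 2.479% | 2.48% |
| 25.0% | 2.684% | 2.68% |

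All eight match. A continuity-corrected version gives 0.487% in the first row and does not match, so the plain normal approximation was used.

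**Step 2: actual coverage at p = 0.5%.** Expected events: 1000 × 0.005 = 5. For x events the interval is x/n ± 1.96 × √((x/n)(1 − x/n)/n). Its limits near the two ends are:

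- x = 2: upper limit 0.477%, below 0.5%. The same holds for x = 0 and x = 1.
- x = 3: upper limit 0.639%, above 0.5%.
- x = 11: lower limit 0.454%, below 0.5%.
- x = 12: lower limit 0.525%, above 0.5%.

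The interval therefore contains 0.5% only for 3 to 11 events. With X ~ Binomial(1000, 0.005):

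- P(upper limit below the truth) = P(X ≤ 2) = 0.0067 + 0.0334 + 0.0839 = 0.124
- P(lower limit above the truth) = P(X ≥ 12) = 0.005
- Coverage = 1 − 0.124 − 0.005 = 0.871

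The nominal values are 0.025, 0.025 and 0.95. Because counts are discrete, coverage depends on the exact rate: for true rates from 0.4% to 0.6% it ranges from 85% to 95%, with a mean of 91%. The figure of 87% belongs to 0.5%, the rate that the row tabulates.

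**Step 3: the interval at 5/1000 by three methods.**

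| Method | Lower | Upper | Half-width | Coverage at true 0.5% |
|---|---|---|---|---|
| Normal approximation | 0.06% | 0.94% | 0.44% | 87.1% |
| Wilson | 0.21% | 1.17% | 0.48% | 96.2% |
| Clopper-Pearson | 0.16% | 1.16% | 0.50% | 98.0% |

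The Clopper-Pearson interval reaches 1.16 − 0.50 = 0.66 points above the estimate and 0.50 − 0.16 = 0.34 points below it. One symmetric figure cannot show that.

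**Step 4: the other rows.** The same summation at the seven tabulated rates from 2.5% to 25% gives coverage of 94.2% to 95.3%. At 25/1000 the half-width is 0.97% by normal approximation, 0.98% by Wilson and 1.02% by Clopper-Pearson. These rows do not need correction.

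**Step 5: zero events.** The exact two-sided 95% upper limit for 0/1000 is 1 − 0.025^(1/1000) = 0.37%. The normal approximation gives an interval of zero width.

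**The case against.** The strongest reply is that nothing is miscalculated or hidden. The protocol names its method and the figures follow from it. The planning basis is the cited range of 2.5% to 22%, where the approximation works. The 0.5% row lies outside that range, its half-width changes by only 0.04 to 0.06 points, and no rates are given for the rare reactions listed. All of this stands. It makes the point minor, but it does not give the 0.5% row the 95% property that Section 9.1 claims for it.

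Four stronger readings are tempting, and the protocol does not support them.

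- **A reader might call the 0.44-point band an 87% interval.** The 87% is the coverage of the interval procedure, whose width changes with the data. At a true rate of 0.5%, the estimate falls within 0.44 points of it when there are 1 to 9 events, which happens in 96.2% of samples.
- **A reader might say the precision is understated by half, from 0.66/0.44.** Section 9.1 defines precision as a half-width and states no upper arm. Like for like, the change is from 0.44% to 0.48-0.50%. The 0.66 describes the asymmetry only.
- **A reader might infer that the registry will report limits that are too low.** Section 9.1 uses the approximation for planning. Section 9.2.3 names no interval method for the results, and Section 9.2.1 leaves detail to the SAP, which is not available here.
- **A reader might add that attrition widens every row.** Section 9.2.3 divides patients with an event by patients enrolled, so censoring does not reduce the denominator in that estimator. Loss to follow-up could lower the observed proportion, but that is a different question. The protocol gives no attrition rate to work from.

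**Conclusion.** The point holds as a minor correction confined to one row. Table 2 is arithmetically right, and the rows from 2.5% to 25% stand. In the 0.5% row the nominal 95% interval has about 87% coverage at a true rate of 0.5%, and nearly all of the shortfall is an upper limit that is too low (12.4% of samples against 2.5%). At 5/1000 that limit is 0.94%, against 1.16% by Clopper-Pearson and 1.17% by Wilson.

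The calculation takes the protocol's own setting: 1,000 patients in the denominator, independent binomial outcomes and a true rate of 0.5%. The relevance to uncommon reactions rests on the objective and the special-interest list, since no expected rates are given. The choice of 1,000 patients is not undermined.

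**What to change.** - Recompute Table 2, at least its 0.5% row, with Clopper-Pearson or Wilson limits.
- Show lower and upper limits in place of the single half-width. For the 0.5% row these are 0.16% to 1.16% (Clopper-Pearson) or 0.21% to 1.17% (Wilson).
- Amend the sentence in Section 9.1 that names the normal approximation, and the definition of precision if the half-width column is dropped.
- Optionally, add a note that 0 events in 1,000 patients gives an exact two-sided 95% upper limit of 0.37%.

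The cost is part of one table and a sentence or two. The stated precision becomes slightly less favourable in the 0.5% row, and the sample size and data collection stay as they are.
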